14.3 Vital Signs

Vital signs will include body temperature, resting respiration rate, supine and standing systolic and diastolic blood pressure, and pulse rate. Blood pressure and pulse rate measurements will be taken after the subject rests for 5 minutes in the supine position. The subject will then be asked to stand and blood pressure and pulse rate will be taken after the subject stands for 1 minute and then again after 3 minutes. Subjects unable to stand may be assessed while sitting upright. A drop in SBP of ≥ 20 mmHg or in DBP of ≥ 10 mmHg or if the subject is experiencing lightheadedness or dizziness is considered abnormal and orthostasis should be considered.

Vital signs will be evaluated at all designated study visits. A 15-minute window is permitted for vital sign measurements.

Vital signs will be summarized using descriptive statistics at Baseline and all scheduled post-Baseline visits/timepoints. The change from Baseline values will also be summarized at the scheduled post-Baseline visits/timepoints.

Vital sign values will be considered PCI if they meet the criteria listed in [Table 4](#). The number and percentage of subjects with post-Baseline vital signs that are PCI will be summarized by treatment group at each post-Baseline visit and for overall post-Baseline. For the overall post-Baseline summaries, all post-Baseline values will be considered, including unscheduled and out of window values. Subjects with multiple PCI values for a given parameter will be counted only once for that parameter. For the by-visit summary, the numerator for the percentage is the number of subjects with a post-Baseline PCI vital sign for the given parameter, visit and treatment group, and the denominator is the number of subjects with non-missing values for the given parameter, visit and treatment group. For the overall post-Baseline summary, the numerator for the percentage is the number of subjects with at least 1 post-Baseline PCI vital sign for the given parameter and treatment group, and the denominator is the number of subjects with at least 1 post-Baseline vital sign for the given parameter and treatment group. A listing of overall and of subjects with any PCI vital sign values will be provided.

Table 4 Criteria for Potentially Clinically Important Vital Signs

Vital Sign Parameter	Unit	Criteria ^a		
		Observed Value	And/Or	Change Relative to Baseline
Systolic blood pressure (supine)	mmHg	≥180	And	Increase of ≥20
		≤90	And	Decrease of ≥20
Systolic blood pressure (standing or sitting)	mmHg	≥180	And	Increase of ≥20
		≤90	And	Decrease of ≥20
Diastolic blood pressure (supine)	mmHg	≥105	And	Increase of ≥15
		≤50	And	Decrease of ≥15
Diastolic blood pressure (standing or sitting)	mmHg	≥105	And	Increase of ≥15
		≤50	And	Decrease of ≥15
Systolic blood pressure (supine to standing)	mmHg			Decrease ≥ 20 mmHg
Diastolic blood pressure (supine to standing)	mmHg			Decrease ≥ 10 mmHg
Pulse (supine)	bpm	≥120	And	Increase of ≥15
		≤50	And	Decrease of ≥15
				Decrease of ≥7%
Pulse (standing or sitting)	bpm	≥120	And	Increase of ≥15
		≤50	And	Decrease of ≥15
				Decrease of ≥7%

^a A post-baseline value is considered as a PCI value if it meets both criteria for observed value and change from baseline.

In addition, the following additional PCI criteria for orthostatic hypotension, significant bradycardia will be flagged, listed, and summarized:

- Orthostatic hypotension: decrease in systolic blood pressure (SBP) ≥20 mmHg or diastolic blood pressure (DBP) ≥10 mmHg after transitioning from the supine position (after resting for 5 minutes) to standing at 1 or 3 minutes with or without symptoms such as light headedness or dizziness and not explained by dehydration, illness, or medications.
- Significant bradycardia: defined as heart rate of ≤45 beats per minute (BPM) on an ECG, or pulse decrease of ≥25% from Baseline with resulting heart rate < 60 BPM.

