5 DATA HANDLING CONVENTIONS

All data collected in the study will be listed.

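### Does SAP Table 4 need correcting because its two 7% pulse lines do not fit the table's own footnote?

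*SAP*

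**What the plan says.** SAP 14.3 ties the flag to the table: "Vital sign values will be considered PCI if they meet the criteria listed in" Table 4. Flagged subjects are then counted by treatment group, at each post-baseline visit and overall, and listed.

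For each pulse position, Table 4 prints three lines:

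- high: observed 120 bpm or more, And, a rise of 15 or more;
- low: observed 50 bpm or less, And, a fall of 15 or more;
- a third line, "Decrease of ≥7" per cent, with the observed-value and And/Or cells blank.

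Footnote a reads: "A post-baseline value is considered as a PCI value if it meets both criteria for observed value and change from baseline". Two blood pressure rows, "Systolic blood pressure (supine to standing") and "Diastolic blood pressure (supine to standing"), also have no observed-value criterion.

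The same section covers pulse in other ways. On vital signs generally it says: "The change from Baseline values will also be summarized at the scheduled post-Baseline visits/timepoints". It also adds a separate significant-bradycardia flag, one arm of which is a "pulse decrease of ≥25% from Baseline with resulting heart rate < 60 BPM". SAP section 5 states: "All data collected in the study will be listed".

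**The concern.** A PCI criterion should say exactly which values it flags. Taken literally, footnote a makes the 7% lines inert, because they carry no observed-value condition to meet. If the limit of 50 bpm is meant to carry down, the table does not say whether the 7% line is an alternative to the 15 bpm fall or an addition to it. If the line stands alone, it contradicts the footnote and would flag ordinary visit-to-visit variation. Two programmers could therefore produce different pulse PCI counts from the same data. Bradycardia is among the adverse events of interest in SAP 14.1, so a low-pulse count has some relevance. SAP section 19 revises only efficacy analyses, so this safety output still stands after the early termination.

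**Working it through.** **Inputs from the documents.** The pulse criteria and footnote a are from SAP Table 4. The three scheduled post-baseline vital-sign visits (Weeks 1, 2 and 4) are from SAP Appendix A. The 61 randomized subjects are from SAP section 1, so 61/3 ≈ 20 per arm.

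**Assumed inputs (in neither document).** Mean pulse 65 to 75 bpm, between-subject SD 9, within-subject SD 4 to 6, no drug effect, one supine reading at each of the three visits.

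**Step 1: how the low line and the 7% line relate.** If the observed value is 50 or less and the fall is 15 or more, then

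fall / baseline = fall / (observed + fall) ≥ 15 / (50 + 15) = 15/65 = 23.1%.

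So every value meeting the low line also meets a 7% fall. The reverse is not true. At an observed 50 bpm the low line needs a baseline of at least 65. A 7% fall needs a baseline of at least 50/0.93 = 53.8, that is 54 in whole beats. With an observed value of 50, the lines disagree only for baselines of 54 to 64.

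**Step 2: the direct readings.**

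| Reading of the 7% line | Fits footnote a? | Consequence |
|---|---|---|
| A. Footnote literal, no observed value to meet | yes | 7% line flags nobody |
| B. ≤50 carried down, fall ≥15 **or** ≥7% | yes | low line nested inside the 7% line |
| C. ≤50 carried down, fall ≥15 **and** ≥7% | yes | 7% line adds nothing; same output as A |
| D. Stand-alone 7% fall | no | low line nested; most values flagged are not low |

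These four are not the only possibilities. Carrying down 120 or more instead (a pulse still at least 120 after a 7% fall) meets the footnote and leaves all three lines active. It is implausible, since it skips the line directly above, but it means one cannot say that no reading works.

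**Step 3: size.** Simulated share of subjects with any supine pulse PCI value (high, low and 7% lines together), 400,000 subjects per scenario:

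- A and C: 0.05% to 3.4%, identical in every scenario.
- B: 0.8% to 12.9%.
- D: 35% to 53%, or about 7 to 11 subjects of 20.

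B minus A is 0.73 to 9.46 percentage points. Multiplied by 20 subjects, that is 0.15 to 1.89 subjects per arm. At mean 70 and within-subject SD 5, it is about 0.6–0.7% against 3.9–4.2%, or roughly 0.7 subject per arm. Widening the within-subject SD to 3–10 gives 0.1 to 2.0 subjects per arm.

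**Step 4: why D is large.** For one reading with no true change, P(fall ≥7%) = Φ(−0.07 × baseline / (SD × √2)). At baseline 70 and SD 6 this is Φ(−4.9/8.49) = 28.2%. With SD 4 to 8 and baseline 60 to 80 it runs from about 16% to 36% per reading.

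**Limits of the model.** Unscheduled readings would raise the shares and missed visits would lower them. Standing pulse is a separate Table 4 parameter counted on its own, so it does not enter the supine figures.

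**The case for a change.** The strongest case for a correction is that an analysis plan should define its own PCI rule and not leave it to programming. Even if the blank cells are a vertically merged entry for 50 bpm or less, the reader still cannot tell *or* from *and*. The supine-to-standing blood pressure rows show that change-only rows do exist in this table, so D cannot be dismissed out of hand, and D would flag a third to a half of subjects from noise alone.

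Part of this stands. The connector is not stated, and footnote a does not literally fit the 7% lines or the two posture rows.

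The rest is weaker than it looks. The posture rows describe a change between positions at one visit, a different kind of parameter with no paired observed-value lines, so they are thin support for D, which the footnote rules out for pulse. Nor is nesting an error in this SAP. It tabulates QTc above 450 and above 480 beside the bands (14.4), and ALT and AST at both 3 and 2 times the upper limit of normal (14.2, where the second tier sits in a separate list). Reading B is a nested pair of the same kind. Table and listing specifications are kept in a separate document (SAP section 1), where a programmer would settle the connector.

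**Conclusion.** This is a gap in one descriptive table that analysts can fill sensibly, and no change to the plan is needed. The direct readings compatible with footnote a differ by about 0.1 to 1.9 flagged subjects per arm of 20, given the assumed pulse distribution. The 35% to 53% figure belongs only to a reading the footnote excludes.

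Nothing rests on the choice. Protocol 9.5.5 rules out hypothesis tests on safety endpoints, and the cardiovascular criteria in Protocol 4.5.1.2 do not use a 7% pulse fall. Falls in pulse are also visible through the change-from-baseline summaries, the significant-bradycardia flag, ECG heart rate (SAP 14.4) and the bradycardia adverse-event term (SAP 14.1). Because the data are listed, the count can be recomputed under any reading.

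There is also no single right edit. Deleting the lines, giving them a condition, or naming them as change-only would produce different counts, and that choice belongs to the sponsor. A line in the table specification or a table footnote saying how the 7% lines were applied would be good housekeeping, but no conclusion of the trial would be unsound without it.

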14.4 Electrocardiogram (ECG)

12-lead ECGs are collected at Baseline (Week 0) both predose and 1 hour postdose (the first dose of the day), Week 1, Week 2, and Week 4 (EOT)/ET. Observed values of ECG variables (e.g., heart rate, PR interval, QRS interval, QT interval, and QTc interval) and the changes

from Baseline at each assessment time point will be summarized by treatment group.

QTcB and QTcF will also be categorized into the following categories (msec) and the number and percentage of subjects in each category will be summarized by treatment group at each visit and for the overall post-Baseline maximum:

- Observed: ≤ 450 , $451 - \leq 480$, $481 - \leq 500$, and >500 ; >450 ; >480 .
- Change from Baseline: ≤ 10 , $11 - 30$, $31 - 60$, and >60 ; >30 .
- QTcF result >470 ms for males, >480 ms for females.
- QTcF increases ≥ 60 ms from Baseline.

For cardiologist's interpretations, the number and percentage of subjects with ECG results that are determined as normal or abnormal will be summarized at scheduled visits. The overall post-baseline worst interpretation will also be summarized (i.e. if a subject has one or more post-baseline ECG results that is/are considered as abnormal, this subject will be counted in the abnormal category). Cardiologist's interpretations will also be summarized in a shift table. The shifts from Baseline to overall post-Baseline worst interpretation will also be presented. For the by-visit shift summary, the denominator is the number of subjects with non-missing cardiologist's interpretation at Baseline and the given visit for the given treatment group. For the summaries of shift from Baseline to the overall post-Baseline worst interpretation, the denominator is the number of subjects with non-missing Baseline and at least 1 post-Baseline cardiologist's interpretation for the given treatment group.

Electrocardiogram variable values will be considered PCI if they meet the criteria listed in [Table 5](#). The number and percentage of subjects with post-baseline PCI values will be summarized by treatment group at each post-Baseline visit and for overall post-Baseline. For the by-visit summary, the numerator for the percentage is the number of subjects with a post-Baseline PCI ECG for the given parameter, visit and treatment group, and the denominator is the number of subjects with non-missing values for the given parameter, visit and treatment group. For the overall post-Baseline summary, the numerator for the percentage is the number of subjects with at least 1 post-Baseline PCI ECG for the given parameter and treatment group, and the denominator is the number of subjects with at least 1 post-Baseline ECG value for the given parameter and treatment group. A listing of overall and of all subjects with any PCI ECG values will be provided.

Table 5 Criteria for Potentially Clinically Important ECG Values

ECG Parameter	Unit	High PCI Criteria
QRS Interval	msec	≥120
PR Interval	msec	≥220
QTcB or QTcF	msec	>500
QTcB or QTcF: change from baseline	msec	>60

14.5 Physical Examination

Physical examinations are performed at Baseline (Week 0), Week 4 (EOT)/ET. Physical examination results (normal, abnormal, and not done) will be summarized in a frequency table by treatment group, body system and visit. A listing of overall physical examination data will be listed.

14.6 Other Safety Variables

14.6.1 Suicidality Based on C-SSRS

The event counts and the number and percentage of subjects reporting any post Baseline suicidal ideation, suicidal behavior, or suicidality will be tabulated by treatment group. The event counts and the number and percentage of subjects reporting any post-Baseline non-suicidal self-injurious behavior will also be tabulated. For calculating the percentages, the denominator will be the number of subjects in the Safety Analysis Set.

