4.4 Subject Withdrawal of Consent

In accordance with the Declaration of Helsinki and other applicable regulations, a subject has the right to withdraw from the study at any time, and for any reason, without prejudice to his or her future medical care.

If the subject decides to withdraw consent from all components in the study, this must be documented and no additional assessments will be performed. If the subject wants to discontinue treatment and agrees to the evaluations specified at the EOT/ET visit and/or at safety follow-up (whichever is applicable), as outlined in [Table S-1](#), the agreed assessments should be conducted. The subject's reason for wanting to discontinue treatment and the

agreement to continue with the applicable assessments for study termination must be documented.

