4 ANALYSIS SETS

Safety Analysis Set

The Safety Analysis Set includes all randomized subjects who received at least one dose of study drug (ACP-044 or placebo). Subjects will be analyzed based on the treatment that they actually received. The Safety Analysis Set will be used for all safety analyses.

Full Analysis Set

The Full Analysis Set includes all randomized subjects who received at least one dose of study drug and with baseline pain assessments and at least one post-baseline pain assessment. The Full Analysis Set will be used for the analysis of all efficacy endpoints. Subjects will be analyzed based on their randomized treatment assignment.

Pharmacokinetics Analysis Set

The Pharmacokinetics Analysis Set includes all subjects with at least one measurable ACP-044 plasma concentration. The Pharmacokinetics Analysis Set will be used for ACP-044 plasma concentration summaries.

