5.2.7 Columbia-Suicide Severity Rating Scale (C-SSRS)

The C-SSRS is assessed at Baseline, Day 7, Day 14, and Day 28 (EOT/ET).

The C-SSRS version assessing information since the last visit will be completed at all visits (including the Baseline visit).

There are 5 questions about suicidal ideation, representing 5 types of suicidal ideation: wish to be dead; non-specific active suicidal thoughts; active suicidal ideation with any methods (not plan) without intent to act; active suicidal ideation with some intent to act, without specific plan; active suicidal ideation with specific plan and intent. If a subject answers “yes” to any of these 5 questions, this subject will be counted as having suicidal ideation.

There are 5 questions about suicidal behavior, representing 5 types of suicidal behavior: preparatory acts or behavior; aborted attempt; interrupted attempt; actual attempt; suicide. If a subject answers “yes” to any of these 5 questions, this subject will be counted as having suicidal behavior.

Suicidality is defined as a subject who reported at least 1 occurrence of suicidal ideation or at least 1 occurrence of suicidal behavior at any post-Baseline visit including unscheduled and out of window visits.

Missing C-SSRS item scores will not be imputed.

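### C-SSRS percentages in effect count dosed subjects with no post-Baseline C-SSRS as free of suicidality, unlike the SAP's overall summaries for labs, vital signs and ECG

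*SAP*

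**What the plan says.** SAP 14.6.1 defines the table: "The event counts and the number and percentage of subjects reporting any post Baseline suicidal ideation, suicidal behavior, or suicidality will be tabulated by treatment". It then fixes the denominator: "For calculating the percentages, the denominator will be the number of subjects in the Safety Analysis Set".

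SAP Section 4 sets the entry condition for that set: "The Safety Analysis Set includes all randomized subjects who received at least one dose of study drug (ACP-044 or placebo"). No post-Baseline assessment is required.

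SAP 5.2.7 defines suicidality by at least one report of ideation or "at least 1 occurrence of suicidal behavior at any post-Baseline visit including unscheduled and out of window visits". It also gives the timing: "The C-SSRS is assessed at Baseline, Day 7, Day 14, and Day 28 (EOT/ET"). The first scheduled post-Baseline assessment is therefore at Week 1. The schedule in SAP Appendix A shows none at the Day 3 visit.

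For the overall post-Baseline summary of potentially clinically important (PCI) ECG values, SAP 14.4 takes a different line: "the denominator is the number of subjects with at least 1 post-Baseline ECG value for the given parameter and treatment group". SAP 14.2 and 14.3 state the matching rule for laboratory values and vital signs.

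SAP Section 19, which lists the changes made after early termination, alters efficacy analyses only. The rule in 14.6.1 still applies.

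**The concern.** The C-SSRS can detect suicidality only when it is administered. A dosed subject without a post-Baseline C-SSRS adds one to the denominator and can add nothing to the numerator, so the percentage treats that subject as a negative.

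The SAP avoids this for the other scheduled safety measurements named above and gives no reason for treating the C-SSRS differently. At stake is how a named safety endpoint reads in a small trial: SAP Section 1 says 61 subjects were randomized, so one subject is about 5% of an arm. If the arms differ in the share of unassessed subjects, the comparison between them shifts too.

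**Working it through.** The documents state no C-SSRS rate, no case count and no count of unassessed subjects, so there is no plan figure to reproduce. The check is on the rule itself.

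**Can a dosed subject lack a post-Baseline C-SSRS?** Yes.
- Protocol 4.4 on full withdrawal: "If the subject decides to withdraw consent from all components in the study, this must be documented and no additional assessments will be performed". If this happens after the first dose and before Week 1, there is none.
- A subject lost to follow-up (Protocol 4.6) before Week 1, with no early termination (ET) visit, also has none.
- The later safety follow-up does not fill the gap. Protocol 6.8 lists pain, adverse events and medications at the clinic visit, and adverse events and medications at the telephone call. Neither includes the C-SSRS.

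**Formula.** For one arm, let N be the Safety Analysis Set count, u the number with no post-Baseline C-SSRS, and x the number of subjects with a positive report.
- SAP rate = x / N
- Rate among those assessed = x / (N − u)
- SAP rate ÷ assessed rate = (N − u) / N = 1 − u/N

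So the SAP rate is never above the assessed rate. It is below it when u > 0 and x > 0, and the relative shortfall equals the unassessed share u/N. If x = 0, both are 0%.

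**Assumed inputs.**
- N = 20 per arm: 61 randomized at 1:1:1 is 61/3 = 20.3, taking all as dosed.
- u from 0 to 4. The top value is the planning discontinuation rate in SAP 3.5 (20% × 20 = 4), with every discontinuation falling before Week 1 and no ET or unscheduled assessment. It is a bound under that rate, not an estimate.

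| u | SAP rate, x = 1 | Assessed rate, x = 1 | SAP rate, x = 2 | Assessed rate, x = 2 |
|---|---|---|---|---|
| 0 | 1/20 = 5.00% | 1/20 = 5.00% | 10.00% | 10.00% |
| 1 | 5.00% | 1/19 = 5.26% | 10.00% | 10.53% |
| 2 | 5.00% | 1/18 = 5.56% | 10.00% | 11.11% |
| 4 | 5.00% | 1/16 = 6.25% | 10.00% | 12.50% |

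With one case the absolute gap is 0.26 to 1.25 percentage points for u from 1 to 4. At the planned 80 per arm it would have been smaller: one case is 1.25%, against 1.32% (u = 4), 1.39% (u = 8) or 1.56% (u = 16).

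**Effect on the comparison.** Take one case in each of two arms of 20.
- u = 4 on ACP-044 and 0 on placebo: the SAP shows 5.0% versus 5.0%; among those assessed it is 6.25% versus 5.0%.
- u = 0 on ACP-044 and 4 on placebo: the SAP again shows 5.0% versus 5.0%; among those assessed it is 5.0% versus 6.25%.
- Equal u/N in both arms: the ratio of the two rates is unchanged.

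**The case against.** The rule is explicit, and SAP Sections 4 and 14 assign the Safety Analysis Set to all safety analyses. The C-SSRS table counts subjects reporting events, much like the adverse event tables in SAP 14.1. Labs, vital signs and ECG are measured values judged parameter by parameter, so a denominator of subjects with a value suits them more naturally. Nothing in the SAP requires one denominator throughout.

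The number unassessed is also likely to be small. The C-SSRS is scheduled at ET and generally recorded at unscheduled visits (Protocol 6.9), and unscheduled and out-of-window visits count. Protocol 4.5.2 asks for every reasonable effort to complete the ET visit. Event counts and numbers of subjects are tabulated and all data are listed, so no case is hidden. Changing the denominator does not recover unobserved events either.

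Most of this stands as a limit on size. It does not supply a reason for the denominator. The analogy with adverse events is weak, because those are asked about at each visit and followed through the safety period (Protocol 7.3 and 7.4.1), whereas the C-SSRS yields information only when given. That the fix recovers nothing is a reason to show the unassessed count as well.

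A reader might go further in three ways that the documents do not support:
- **That the rule always favours the drug.** It applies to every arm, so the comparison can move in either direction.
- **That SAP 5.2.7 contradicts it.** That section says "Missing C-SSRS item scores will not be imputed". This concerns items within an assessment; a stated denominator imputes no item.
- **That early exits are where unobserved events are most likely.** No passage says so.

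**Conclusion.** The point holds as a minor reporting weakness. Under SAP 14.6.1 the rate in any arm is the assessed rate times (1 − u/N): never overstated, and understated when at least one dosed subject is unassessed and at least one case exists. It departs, without explanation, from the SAP's denominator for the overall post-Baseline PCI summaries of labs, vital signs and ECG.

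The size rests on two assumptions: about 20 subjects per arm, and an unassessed count that the documents do not give. With one case, the reported 5.0% would be 5.3% to 5.6% for one or two unassessed subjects, and 6.25% at the bound of four. If nobody is unassessed, or there are no cases, the percentage is the same under either denominator.

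It is tempting to put confidence limits around a zero count to make the effect look larger. The plan produces none for this table, and Protocol 9.5.5 rules out formal testing of safety endpoints, so they are not part of the case.

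**What to change.** Replace the denominator sentence in SAP 14.6.1 with: *The denominator will be the number of subjects in the Safety Analysis Set with at least 1 post-Baseline C-SSRS assessment.* Add a row showing, by arm, the number of Safety Analysis Set subjects without one.

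If the present denominator is kept, the least that would serve is to print the number assessed in each arm beside the percentage.

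The cost is one sentence and one table row. The only downside is that some percentages may be slightly less favourable.
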